## 5.5 PREMATURE TERMINATION OR SUSPENSION OF THE STUDY OR A STUDY SITE

The study or a study site can be prematurely terminated or suspended by the sponsor. Reasons for termination of the study or a study site may include, but are not limited to, the following:

- Participant enrollment is unsatisfactory.
- The risks and benefits of continuing the study have been reassessed, and the risks outweigh any potential benefits.
- The incidence of AEs constitutes a potential health hazard to the participants.
- New scientific data do not justify a continuation of the study.
- The investigator or study site exhibit serious and/or persistent non-adherence to the protocol, the Declaration of Helsinki, EN ISO 14155, and/or applicable regulatory requirements.
- The sponsor decides to terminate the study at any time for any other reason.

Furthermore, the study may be prematurely ended if the regulatory authority or the IRB has decided to terminate or suspend approval for the study, the study site, or the investigator.

If the study is prematurely terminated or suspended for any reason, the investigator must inform the participants and assure appropriate follow-up treatment. Within the timeframes noted in applicable regulations, the sponsor will promptly inform the investigators, study sites, the IRB, and regulatory authorities of the termination or suspension of the study, as well as provide reasons for the action.

## 6. STUDY PROCEDURES AND SCHEDULE

### 6.1 STUDY IMAGES

Standardized baseline and follow-up images will be taken. All participant photos must be taken in a standardized format. Review each item on the checklist below every time study photos are taken to ensure “Standardized Images” are taken.

#### PRIOR TO TAKING PHOTOGRAPHS:

- Natural Skin; skin washed, and no make-up
- Jewelry removed
- For any body part being treated, ensure a black background is in place
- Treatment area may be marked with a surgical marker prior to photographs

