## 4.3 STUDY ENDPOINTS

### 4.3.1 PRIMARY ENDPOINT

The primary endpoint of this study is:

1. Group A: Selection of post-treatment images when randomized with baseline images as assessed by blinded evaluators
2. Group B: Evaluation of histological samples taken via punch biopsies to observe treatment effect and wound healing.

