#### 4.4 SUCCESS CRITERIA

The study will be considered a success if the following criteria are met:

Group A: Clinical Treatment Arm

1. Blinded evaluators are able to correctly identify the post-treatment image at least 80% of the time
2. The adverse event and side effect profile are acceptable

Group B: Biopsy Arm

1. Wounds induced by the treatment device appropriately healed as assessed by histology.

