#### AFTER TAKING PHOTOGRAPHS (*before participant leaves the office*):

- Ensure all views have been taken
- Ensure all photographs are in focus
- Ensure lighting is consistent
- Ensure all follow-up photographs are similar to baseline images in views, angles, lighting, placement, and distance.

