## 8. CLINICAL MONITORING

Clinical site monitoring is conducted to ensure that the rights and well-being of human participants are protected, that the reported trial data are accurate, complete, and verifiable, and that the conduct of the trial is in compliance with the currently approved protocol/amendment(s), with GCP, and with applicable regulatory requirement(s).

- Monitoring for this study will be performed by the Sponsor or Sponsor contract monitor.
- Clinical study site and data monitoring will be conducted via both centralized and on-site monitoring.
  - Centralized data monitoring will focus primarily on:
    - Ongoing, real-time review of clinical data supporting safety, and primary and secondary study-defined endpoints, specifically:
      - Tracking the occurrence of adverse events and expected treatment effects.
    - Ongoing, real-time review of clinical data as entered on Case Report Forms (CRF):
      - Initial study consent was obtained for all enrolled participants;
      - Eligibility for study participation of all enrolled participants;
      - Verification of protocol compliance and data completeness.
    - Ongoing, real-time evaluation of data trends to identify outliers, unexpected trends, or holes in data collection;
    - Ongoing, real-time evaluation of study photographs.
  - Centralized monitoring requires timely data entry and timely uploading of completed CRFs to the study HIPAA compliant cloud-based system (eg ,no later than seven working days after a study visit has occurred).
  - On- site monitoring visits will include:
    - Review of primary/secondary endpoint data source documents;
    - Confirmation that participant randomization is being completed appropriately (if applicable);
    - Confirmation that study blinding is maintained (if applicable);
    - Confirmation of appropriate execution of the PGAIS, SGAIS, PSQ, or other study-specific scales;
    - Note any other study-specific study design items requiring on-site confirmation.
  - General on-site monitoring tasks will include:
    - Review of study conduct and progress at each investigative site (eg, protocol compliance, participant recruitment, etc).
    - Confirmation that written informed consent was obtained and documented at the time

of screening, using an appropriate version of an IRB-approved ICF, and participant eligibility is confirmed.

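### Optional skin marking before study photographs could give away which image is post-treatment in the Group A blinded read, and no rule requires marks to match or be absent

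*Combined protocol and SAP*

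**What the plan says.** The Group A primary endpoint (Section 4.3.1) is "Selection of post-treatment images when randomized with baseline images as assessed by blinded evaluators". The matching efficacy criterion in Section 4.4 is "Blinded evaluators are able to correctly identify the post-treatment image at least 80% of the time"; the other Group A criterion there concerns safety.

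Section 6.1 governs the images. It states that "All participant photos must be taken in a standardized format" and tells sites to "Review each item on the checklist below every time study photos are taken". Under the items to check before photographing, that checklist includes: "Treatment area may be marked with a surgical marker prior to photographs". The permission is not tied to a visit, a study group or a type of image, and no removal step follows. After photographing, sites must "Ensure all follow-up photographs are similar to baseline images in views, angles, lighting, placement, and distance". Skin marks are not among those five attributes.

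Other controls are general. Section 8 provides for "Ongoing, real-time evaluation of study photographs" and for an on-site check that blinding is maintained, where applicable. Section 9.1 restricts the efficacy analysis to participants with evaluable post-treatment images, but does not define evaluable.

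**The concern.** In a forced choice between a before and an after image, the result is valid only if nothing but treatment effect separates the two. Marks in both images, or in neither, give no obvious cue. A mark in one image only may tell the evaluator which image was taken around a treatment session.

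The schedule in Table 5 gives a plausible reason for asymmetry. In Group A the first scheduled photographs fall at a treatment visit, where Section 6.3.2 has the clinician identify the area to be treated. The 30- and 90-day photographs fall at visits without device treatment. That the reason to mark differs between these visits is an inference; the plan does not say why marking is allowed.

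At stake is the only efficacy success criterion for Group A. A mark read correctly raises the identification rate and a mark misread lowers it. Either way the rate no longer measures visible change alone, and a cue cannot be taken out of a read already done.

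**Working it through.** **Text check.** Setting the relevant places side by side:

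- Section 6.1, before photographing: marking is optional.
- Section 6.1, opening: the checklist applies at every photo session, so the option is open separately at baseline and at each follow-up.
- Section 6.1, after photographing: five attributes must match. *Placement* stands with views, angles and distance and most naturally means positioning.
- Section 6.1, skin preparation: skin is to be natural, washed and free of make-up, but the same list permits the marker, so this item does not exclude marks.
- Section 6.3.6: pre-treatment marking and photographing is described for Group B only, with no rule on follow-up marks.
- Sections 8 and 9.1: neither names marks, cropping or masking.

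One-sided marking therefore complies with the plan as written. Appendices A and B are attached separately and were not available.

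**Illustration of size.** The plan gives no figure to reproduce here: no power calculation, number of evaluators or expected identification rate. The only inputs from the documents are the 80% bar (Section 4.4) and the Group A ceiling of 180 (Section 4.1). Everything else is assumed:

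- u: correct rate in pairs without a cue
- s: share of pairs marked on one side only
- c: chance that the evaluator picks the post-treatment image in such a pair
- one independent read per subject

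The expected correct rate is p = u(1 − s) + cs, so the cue inflates the rate only if c > u. Success needs X ≥ 0.8 × 180 = 144, with X ~ Binomial(180, p).

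| u | s | c | p | P(X ≥ 144) |
|---|---|---|---|---|
| 0.75 | 0 | – | 0.750 | 0.07 |
| 0.75 | 0.01 | 1.0 | 0.7525 | 0.08 |
| 0.75 | 0.05 | 1.0 | 0.7625 | 0.14 |
| 0.75 | 0.10 | 1.0 | 0.775 | 0.24 |
| 0.75 | 0.10 | 0.9 | 0.765 | 0.15 |
| 0.75 | 0.10 | 0.5 | 0.725 | 0.01 |
| 0.75 | 0.20 | 1.0 | 0.800 | 0.54 |
| 0.75 | 0.20 | 0.9 | 0.780 | 0.29 |
| 0.75 | 0.20 | 0.5 | 0.700 | 0.002 |
| 0.85 | 0 | – | 0.850 | 0.97 |
| 0.85 | 0.10 | 1.0 | 0.865 | 0.99 |
| 0.85 | 0.10 | 0.5 | 0.815 | 0.73 |
| 0.85 | 0.20 | 0.5 | 0.780 | 0.29 |

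Example for the fourth row: 0.75 × 0.90 + 1.0 × 0.10 = 0.775.

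For a device with no visible effect (u = 0.50), the share needed for an expected 80% is s = (0.80 − 0.50)/(c − 0.50). That is 0.30/0.50 = 60% at c = 1.0 and 0.30/0.40 = 75% at c = 0.9.

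Because 180 is a ceiling, the case of 90 evaluable pairs (at least 72 correct) was also run. With u = 0.75 and c = 1.0, the chance of success is 0.17, 0.34 and 0.56 at s = 0, 10% and 20%.

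**The case against.** The strongest case on the other side is that harm needs a chain of events that the documents do not show. A site must mark, mark only one image of a pair, that image must enter the read, and the evaluator must use the mark. The study is labelled a pilot, and the requirements for standardized, similar photographs, together with the photo review in Section 8, would lead many sites to avoid mismatched marks. The one place that calls for marking with photographs is Section 6.3.6, for Group B, whose endpoint is histology; the checklist line may exist mainly for that group. The illustration uses invented inputs, and its main case sits just below the 80% bar, where any shift looks large. Finally, if marks in both images are harmless, matching would be enough and a ban goes further than needed.

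Much of this stands. The risk is conditional, its direction is not fixed, and it matters mainly when the true rate is near 80%: at u = 0.85 with correctly read marks in 10% of pairs, the chance of success moves only from 0.97 to 0.99. Matching is a legitimate minimum remedy.

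It does not close the gap. The checklist line is not limited to Group B. The general controls do not make one-sided marking a deviation, so a monitor would have no rule to cite.

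**Conclusion.** The concern holds. The plan permits marking at each photo session and, in the supplied documents, neither requires marks to match within a pair nor keeps them out of the blinded read. This is an unaddressed risk to the blinding of Group A's primary endpoint; no bias has been shown.

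The size is unknown. Under the assumed inputs, correctly read marks matter most for a device just under the bar, and misleading marks can cost a device above it its success. Occasional marking would not make a device with no visible effect succeed. These statements rest on one independent read per subject and on assumed values of u, s and c. The point is worth fixing because it touches the only Group A efficacy criterion and the remedy is cheap.

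**What to change.** Replace the marking line in the Section 6.1 checklist with, for example: *Photographs for the blinded read are taken before any skin marking at every visit; marked photographs may be taken afterwards for treatment mapping only.* Add absence of skin marks to the list of attributes on which follow-up and baseline photographs must agree, and make it an item in the photograph review already planned in Section 8. For pairs already collected with a mark in only one image, report the identification rate with and without them.

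The cost is two checklist lines, one review item, a small change in photo workflow and a second set of photographs where a site wants a marked image. Evaluators may also lose a guide to the treated area.

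If marked images are wanted in the read, the minimum alternative is to add skin marking to the matching list so that both images of a pair agree. That takes a few words and no second set, but relies on sites reproducing the marks at follow-up.

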#### WHILE TAKING PHOTOGRAPHS:

- Ensure photograph is in focus
- For facial images, take five images: front, left 45°, left 90°, right 45°, right 90°
- For all other body parts, take one to three images to adequately capture the participant

#### AFTER TAKING PHOTOGRAPHS (*before participant leaves the office*):

- Ensure all views have been taken
- Ensure all photographs are in focus
- Ensure lighting is consistent
- Ensure all follow-up photographs are similar to baseline images in views, angles, lighting, placement, and distance.

### 6.2 STUDY SCHEDULE

Table 5: Study Schedule

Group A – Clinical Treatment Arm – Schedule and Planned Activities

	Screening	Treatment	Post Treatment Follow-Up (optional) 1-7days post Tx	Follow-Up 30-day post final TX	Follow-Up 90-day post final TX
Visit Number	1	2, 4, 6, 8, 10	3, 5, 7, 9, 11	12	13
Study Day #	0	0 – 140	1-147	170 (±7)	230 (±14)
Screening Activities	X				
Pregnancy Test	X	X			
Photographs		X	X	X	X
Device Treatment		X			
Biopsy (optional)		X	X	X	X
Adverse Event Assessment		X	X	X	X
Subject Evaluations				X	X
Physician Evaluation				X	X

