## PROTOCOL SYNOPSIS

Protocol Number:	LMI22001
Protocol Title:	Safety and Efficacy of the Mosaic Ultra Device
Investigational Devices:	Mosaic Ultra
Development Phase:	Pilot
Study Objective:	Evaluate the Safety and Efficacy of the Mosaic Ultra 1550nm system for the treatment of skin tone and texture, facial rejuvenation, photoaging, wrinkles, scars, stretch marks, acne vulgaris and hair loss.
Brief Study Overview:	
Prospective, Multi-Site, Non-Randomized study of up to 210 participants in two treatment groups
 
 
• Group A: Clinical Treatment Arm (n=180)
 
• Group B: Biopsy Arm (n=30)
 
 
Subject's in Group A will be treated with the device with the recommended parameters based on pre-clinical testing and similar device parameters. Subjects will receive up to 5 treatments and then attend follow-ups 30 and 90-days post treatment. Subject's may be asked to participate in an optional biopsy portion of this arm
 
Subject's in group B will be treated at pre-determined parameters based on regulatory body requirements. Subjects will return up to 3 months post treatment. 5 Biopsies will be collected prior to treatment and throughout the follow-up periods.

Number of Sites Enrolling Participants:	3 sites located in the United States
Sample Size:	N = up to 210 treated participants
Participant Population:	Healthy adults, male and female, at least 18 years old who meet the inclusion and exclusion criteria.
Inclusion Criteria:	
 
• Non-smoking, Male or Female
 
• Age 18 – 60 years old
 
• Understands and accepts the obligation not to undergo any other procedures in the areas to be treated.
 
• Participants who are willing and able to comply with all study participation requirements including returning for follow-up visits and abstaining from exclusionary procedures for the duration of the study.
 
• OPTIONAL - Participants who are willing to undergo biopsies.
 

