Exclusion Criteria:	
 
• Previous surgical or cosmetic procedure to the target area in the last 6 to 12 months that could interfere with the treatment procedure
 
• A study participant must not be pregnant or have been pregnant in the last 3 months
 
• A recent history of smoking (6 months)
 
• Presence of an active skin disease or condition that may affect wound healing (ie. diabetes myelitis; connective tissue disease; radiation therapy; or chemotherapy)
 
• Seizure disorder caused by bright light
 
• A history of thrombophlebitis
 
• A history of acute infections
 
• A history of heart failure
 

	
 
• Cancer, malignant disease, skin pathology, condition, or allergic reactions that could interfere with evaluation or with the use of typical ancillary medical treatments or care used before, during, or after treatments
 
• Received or is anticipated to receive antiplatelets, anticoagulants, thrombolytics, vitamin E, or anti-inflammatories within 2 weeks prior to treatment
 
• Intolerance or allergy to medications that could be prescribed before or after the procedure (eg, antibiotics, anesthesia)
 
• A history of keloids
 
• A history or evidence of poor wound healing
 
• A history of coagulative disorder or current use of anticoagulant drugs within 2 weeks of study participation
 
• Use of steroids within 2 weeks of study treatments
 
• Patients with implanted pacemaker or defibrillator, or metal pins, or prosthetic joints within 4 cm of treatment area
 
• History of psychoneurosis and/or a history of alcohol or drug abuse
 

Primary Endpoint:	
 
• Group A: Evaluation of randomized before treatment and 3-month follow-up images by blinded evaluators
 
• Group B: Complete wound healing following the treatment assessed by collected biopsies.
 

Secondary Endpoints:	
 
• Adverse Event Assessment
 
• Subject satisfaction
 
• Physician satisfaction
 
• Subject Clinical Global Aesthetic Improvement Scale
 
• Physician Clinical Global Aesthetic Improvement Scale
 
• Histological Evaluation
 

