### 6.3.6 ELECTIVE SKIN BIOPSY

Some study-site locations may offer an elective skin biopsy for histological evaluations. The biopsy is considered a safe, low-risk procedure.

The biopsy procedure will involve collecting a small sample of skin from the participant in a discreet location. The punch biopsy, a tool that is usually circular at the extraction site, removes a small, round sample of the epidermis, dermis, and superficial fat (while leaving the extracted layers intact).

Prior to biopsy, participant skin will be cleaned and dried by the treating clinician. The punch instrument is pressed vertically into the skin and then rotated clockwise and counterclockwise between the fingertips. A small “give” can be felt as the device cuts through the epidermis and dermis, down to the superficial layer of subcutaneous fat. The punch biopsy tool is designed to collect tissue very quickly (to reduce pain) and is also designed to reduce the risks of bleeding through precision. However, some temporary pain and minor bleeding can occur at the biopsy site. The biopsy site will be covered with a bandage. There is a small risk of infection and participants must commit to taking care of biopsy site. Participants will be advised to regularly clean the biopsy site with mild soap and water, and to keep it bandaged (a simple bandaid is often enough) until it is fully healed (approximately one month).

For patients participating in the Group B of the study, the intended treatment area of the subject will be marked and photographed prior to treatment and a control biopsy will be taken. The first biopsy (Day 0, control) will be collected at this time. A normal treatment will be then be conducted using pre-determined laser parameters. Subject will then have a biopsy taken immediately post treatment from the treated area.

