#### **6.4 FOLLOW-UP VISITS**

Post-treatment follow-ups may occur up to 7 days post-treatment. These follow-ups are optional and may be conducted in-phone, over email, or in-person as determined by the clinician. If an optional post-treatment follow-up is determined necessary by the clinician the subject will be notified before the end of their treatment visit and the visit will be scheduled at that time. Adverse events will be evaluated at this visit. If subject has elected to participate in the biopsy portion of the study then a biopsy may also be collected at this visit.

In-person follow up visits will occur  $30\pm 7$  and  $90\pm 14$  days post final treatment. Adverse events will be assessed at these visits. Subjects will be asked to rate their satisfaction (Table 3) with their overall results as well as grade their improvement on the CGAIS (Table 4).

Subjects in Group B will then return 3 and 14 days post treatment to have an additional biopsy collected from the treated area. Subject's will then return for a final follow-up for biopsy collection between 19 and 90 days post treatment. Photos will be taken at all visits to ensure proper collection of biopsies as well as to capture the skin response.

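### Group A's optional biopsies share visits with the study photographs, and no rule keeps a biopsy mark out of the images that the blinded evaluators compare

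*Combined protocol and SAP*

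**What the plan says.** The Group A primary endpoint is purely visual. Section 4.3.1 defines it as "Selection of post-treatment images when randomized with baseline images as assessed by blinded evaluators". The synopsis adds the time point: "Group A: Evaluation of randomized before treatment and 3-month follow-up images by blinded evaluators". Section 4.4 sets the bar: "Blinded evaluators are able to correctly identify the post-treatment image at least 80% of the time". The planned size is given in the synopsis as "Group A: Clinical Treatment Arm (n=180)", elsewhere described as a maximum.

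Table 5 for Group A marks "Biopsy (optional)" in the same four columns as photographs: treatment visits, the optional visits 1 to 7 days after treatment, the 30-day visit and the 90-day visit. Section 6.4 confirms this for the optional visits: "If subject has elected to participate in the biopsy portion of the study then a biopsy may also be collected at this visit".

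Section 6.3.6 describes a round punch through epidermis and dermis into superficial fat. On location it says: "The biopsy procedure will involve collecting a small sample of skin from the participant in a discreet location". On aftercare, participants are told to "keep it bandaged (a simple bandaid is often enough) until it is fully healed (approximately one month)".

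The photograph checklist in section 6.1 covers make-up, jewelry, background, focus, views and lighting, and matching follow-up images to baseline. It does not mention biopsy sites or bandages. Section 9 does not mention biopsied Group A participants.

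**The concern.** The endpoint asks whether an evaluator can tell which of two images was taken after treatment. It measures the device only if the device is the sole systematic difference between them. A punch site present in the later image and absent from the earlier one is a second difference, and one that the study itself creates. An evaluator who notices it can pick the later image correctly whether or not the skin has changed.

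The blinding would then be intact in form but not in substance for those pairs, and the identification rate would mix a device effect with a biopsy effect. If the result fell near 80%, nothing in the planned analysis would show how much of it came from biopsied participants.

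**Working it through.** The documents give no power calculation or expected identification rate, so there is no stated figure to reproduce. The check has two parts.

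**1. What could still be visible at the 90-day image.** Inputs are the windows in section 6.4 (30±7 and 90±14 days after final treatment; optional visits up to 7 days, with Table 5 giving 1 to 7) and healing of about one month (section 6.3.6).

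- The 30-day visit falls on days 23 to 37 and the 90-day visit on days 76 to 104.
- Gap from the 30-day visit to the 90-day visit: 76 − 37 = 39 days at least, 104 − 23 = 81 at most.
- Gap from the last optional visit to the 90-day visit: 76 − 7 = 69 days at least, 104 − 1 = 103 at most.

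At about one month of healing, a bandage from any earlier scheduled biopsy should be off by the 90-day photograph. Two cues remain possible: a healed mark from an earlier biopsy, and a fresh site or bandage if a biopsy at the 90-day visit comes before the photograph. Nothing fixes that order for Group A. Section 6.3.6 puts the photograph first only for the Group B control biopsy on Day 0.

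**2. Effect on the 80% criterion.** Let r be the identification rate from the device alone and f the share of pairs with a biopsy cue. Assume every cue is visible and read correctly, with one reading per participant and n = 180. The bar is 0.80 × 180 = 144 correct.

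- Expected observed rate = r + f(1 − r).
- Share needed to bring the expected rate to 80%: f = (0.80 − r)/(1 − r).
- Chance of passing with m = 180f cued pairs: P(X ≥ 144 − m), where X is Binomial(180 − m, r).

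Share needed:

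| r | f | pairs of 180 |
|---|---|---|
| 0.75 | 0.05/0.25 = 20% | 36 |
| 0.70 | 0.10/0.30 = 33% | 60 |
| 0.60 | 0.20/0.40 = 50% | 90 |
| 0.50 | 0.30/0.50 = 60% | 108 |

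Exact binomial chance of at least 144 correct:

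| r | no cue | 5% (m = 9) | 10% (m = 18) | 20% (m = 36) |
|---|---|---|---|---|
| 0.75 | 0.07 | 0.13 | 0.24 | 0.54 |
| 0.70 | 0.002 | 0.006 | 0.017 | 0.11 |

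At r = 0.50 the chance is negligible at all these shares. It is still only 0.036 with half of the pairs cued (m = 90).

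**The case against.** The strongest reply is that the path is narrow. Biopsy in Group A is elective, only some sites may offer it, and most of the biopsy work sits in Group B. Several indications are facial, where a discreet site would usually lie outside the photographed field. Much of this stands, and it limits the size of the problem. It does not close the gap. The location wording is not a framing rule, and for stretch marks or body scars the treated, photographed skin may itself be discreet. Low uptake cannot be assumed either: no number or cap is given, the inclusion list in section 5.2 drops the word optional that the synopsis attaches to biopsy willingness, and section 5.3.1 pays $100 per biopsy.

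A reader might infer more than the documents support, in three ways.

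- *That bandages or open sites would commonly show in the primary image.* The synopsis places that image at three months, and the interval arithmetic leaves only a biopsy taken before the photograph at that same visit.
- *That Group A biopsies must come from treated skin.* The documents say so only for Group B. For Group A it is a plausible inference, because the biopsies are for histology.
- *That the bias must always favor success.* Nothing says that the evaluators know about biopsies. In acne or scar indications, a new round mark could be taken for pathology and the image called the earlier one. Table 5 also allows a biopsy at Visit 2; if it preceded the baseline photograph, both images could carry the mark. Upward is the probable direction, not a certain one.

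**Conclusion.** The concern holds in a limited form. As written, the plan lets a mark made by the study, not by the device, identify the post-treatment image in Group A, and it has no safeguard in photography, image preparation or analysis. The likely cue is a healed punch mark, or a fresh site or bandage if a 90-day biopsy comes before that visit's photograph. The probable effect is to raise the identification rate.

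The size depends on an uptake that the documents do not state. The chances shown are upper-end illustrations: they assume that every cued pair is read correctly, that 180 participants are evaluable and that each contributes one reading. On those terms a cue in 10% of pairs raises the chance of passing from 0.07 to 0.24 at a device-only rate of 75%, but only from 0.002 to 0.017 at 70%. It would be wrong to conclude that biopsies could carry an ineffective device to success at any modest uptake. The damage is to the interpretation of a result near the bar.

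**What to change.** Three changes, none of which alters treatment or says where a participant is biopsied:

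1. In section 6.1 and Table 5, state that Group A study photographs are taken before any biopsy at the same visit.
2. Where a biopsy site falls within a view used for the blinded read, mask or crop the same region in both images of the pair before they are randomized, or leave that view out of the read. Treating both images alike matters, since a mask on one image would itself be a cue.
3. In section 9, report the identification rate with and without biopsied Group A participants, and give the number biopsied.

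The cost is a few lines of protocol text, some image handling, a few lost or cropped views and one extra table.
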